7.2 Study Visits

Biopsy and Fiducial Placement – visit #2

- Weight
- Vitals including blood pressure, pulse, respiratory rate, temperature
- Physical examination
- Guided biopsy
- Fiducial placement

MRI and CT scans for RT SIM – visit #3

- RT CT (with contrast unless contraindicated) for simulation
- Pelvic MRI with Contrast
- Pelvic CT for SIM

SBRT #1 – visit #4

- RT treatment

SBRT #2 – visit #5

- RT treatment

MRI – visit #6

- Pelvic mpMRI with Contrast

SBRT #3 – visit #7

- Adverse events assessment (may be completed by telephone call within 7 days post visit 7)
- RT treatment

Follow up, every 3 months for up to 24 months – visits #8 - #16

- Weight
- Vitals including blood pressure, pulse, respiratory rate, temperature
- Physical examination
- ECOG performance status
- Quality of life Score standard of care IPSS and SHIM Scores
- Adverse events assessment

Post SBRT Follow up Measurements

- PSA to be completed at ALL follow up visits

- DRE to be completed at **ALL** follow up visits
- Serum Creatinine and BUN Blood Draw at **6, 12, and 24** months follow up prior to MRI
- Pelvic MRI to be completed at **6, 12, and 24** month follow up visits with contrast
- EPIC EQ D5, Sexual Medication/Device screening to be completed at **6, 12 and 24** months

Any positive results for staging Post RT (positive digital rectal exam or evidence of biochemical failure using the clinical nadir +2 definition (serum PSA rise above 2ng/mL from the post therapy nadir (Phoenix, Abramowitz 2007) may trigger clinical indication for SOC staging MRI to rule out disease progression. If acquired, this data will be collected for comparison to other serial MRI data. Should a patient be deemed to have failed therapy using the Phoenix criteria (nadir +2ng/mL PSA) the subject/s will be referred for consultation for review of options for salvage therapy, and if the patient elects a second treatment the subject will be taken off study.

7.3 Study Calendar

Study Days	Screen Visit 1	Biopsy and Fiducial Placement Visit 2	MRI* & CT Scans for RT SIM Visit 3	SBRT #1 Visit 4	SBRT #2 Visit 5	MRI Visit 6	SBRT #3 Visit 7	30 days post RT Visit 8	3 mo post RT Visit 9	6 mo post RT Visit 10	9 mo post RT Visit 11	12 mo post RT Visit 12	15, 18 & 21 months post RT Visits 13-15	24 mo Post RT Visit 16
REQUIRED ASSESSMENTS			2-3 wks Post Fiducials	2-3 wks Post SIM										
Informed Consent	X													
Demographics	X													
Medical History	X													
Height	X													
Weight	X	X						X	X	X	X	X	X	X
Vitals (BP Respiration Pulse Temp)	X	X						X	X	X	X	X	X	X
Physical Examination	X	X						X	X	X	X	X	X	X
Concomitant medication assessment including hormone therapy	X							X	X	X	X	X	X	X
ECOG PS	X							X	X	X	X	X	X	X
Baseline Symptoms	X													
IPSS/SHIM QoL Scores	X							Xa	Xa	Xa	Xa	Xa	Xa	Xa
Adverse Event Assessment							X ²	X	X	X	X	X	X	X
CBC w diff /platelets /testosterone	X													
Serum Chemistry ¹	X													
Guided biopsy		X												
Fiducial placement		X												
RT simulation			X											
RT TREATMENT				X	X		X							

Study Days	Screen Visit 1	Biopsy and Fiducial Placement Visit 2	MRI* & CT Scans for RT SIM Visit 3	SBRT #1 Visit 4	SBRT #2 Visit 5	MRI Visit 6	SBRT #3 Visit 7	30 days post RT Visit 8	3 mo post RT Visit 9	6 mo post RT Visit 10	9 mo post RT Visit 11	12 mo post RT Visit 12	15, 18 & 21 months post RT Visits 13-15	24 mo Post RT Visit 16
DISEASE ASSESSMENT														
Pelvic MRI *	X ^{3,4}		X*			X*			X*		X*			X*
Pelvic CT for SIM			X*											
Bone Scan	X ⁴													
PSA	X ⁴								X	X	X	X	X	X
DRE	X ⁴								X	X	X	X	X	X
EPIC EQ D5, Sexual Medication, Device Screening	X									X		X		X

1: Albumin, alkaline phosphatase, total bilirubin, bicarbonate, BUN, calcium, chloride, creatinine, glucose, potassium, total protein, SGOT [AST], SGPT [ALT], sodium. Calculated creatinine clearance will be done if creatinine and/or BUN are abnormal

2: Post treatment A/E assessment may be a telephone call within 7 days post end of therapy.

3: SOC Staging MRI

4: Must have been completed within 90 days of screening visit

a: Physician or Nurse Practitioner consult at post RT visits

* Serum Creatinine And BUN Blood Draw performed prior to pelvic MRI with contrast (mandatory for eligibility)per institutional guidelines.

8.0 Correlative / Special Studies

not applicable

9.0 Safety and Effectiveness Assessments

The primary goal of this pilot study is to determine if MRI with multiparametric sequences mpMRI can be used as a mapping tool for correlation with histopathology results, providing a more informed method for the delivery of focal hypofractionation treatments. Hypofractionated radiation using SBRT is a promising tool for delivery with intent to cure. The use of focal partial prostate SBRT should show lower toxicity, and will be evaluated for equivalent efficacy. A co-primary end point of the pilot study will be to show that patients maintain acceptable HRQOL status as compared to baseline. There will be two co-primary endpoints based on summary scores from the bowel and urinary domains of the EPIC questionnaire. Although HRQOL is collected at multiple time points, it has been decided that EPIC, EQ D5 and Sexual Medication/Device Screening data collected at 6, 12 and 24 months post therapy will be compared to baseline to test the primary hypothesis. The percentage of patients with change in EPIC bowel domain score (baseline to 1-year) that was worse than 5 points and a change in EPIC urinary domain score that was worse than 2 points are felt to be clinically meaningful endpoints to assess for tolerability and safety. A rate for the worse-than-5 point change in bowel score of up to 35% of patients will be considered acceptable, with a rate $\geq 55\%$ specified as unacceptable. Similarly, a rate for the worse-than-2 point change in urinary score of up to 40% will be considered acceptable, with a rate $\geq 60\%$ unacceptable. The PSA results along with serial MRI assessments will be used to test the hypothesis of equivalent disease control compared to historical data for whole gland therapy using SBRT. Standard of care quality of life assessments International Prostate Symptom Score (IPSS) and sexual health inventory for men (SHIM) scores will be acquired as part of the standard care prior to and following SBRT. When collected, this data will be collected and reported.

Analysis of the Primary Endpoints

Treatment efficacy will be analyzed through PSA response, clinical exam, with the addition of serial MRI evaluations. Confirmation of multiparametric MR targets for focal SBRT with image guided biopsy, histopathology and fiducial marker position tracking will be evaluated for reporting accuracy of multiparametric and standard MRI sequences to detect disease. Prostate MRI including T2-weighted, contrast-enhanced, and diffusion weighted imaging along with computer aided detection (CAD) may be used to identify suspicious lesions for targeted biopsy and fiducial placement. Chi-square and cluster analysis will be used to correlate degree of suspicion on MR pulse sequences with incidence of cancer detected on biopsy and subsequently targeted for focal therapy. Post therapy MRI will be used to report response to therapy as either complete, partial, stable or progressive by RECIST criteria.

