
2.0 Study Objectives

Hypothesis: Multiparametric MRI with histopathological correlation can be used to treat sub-volumes of the prostate with focal SBRT in low- and intermediate-risk patients leading to equivalent outcomes as whole-gland therapy with reduced toxicity and improved quality of life.

To validate the above hypothesis in this prospective study, the specific aims include:

- 1) Evaluate the correlation of histopathology findings in comparison to regions of the prostate reported to be suspicious for harboring tumor burden on multiparametric MRI report/s;
- 2) Demonstration of the dosimetric and radiobiological advantages of focal SBRT versus whole-gland radiation therapy;
- 3) Evaluation of clinical outcomes in focal SBRT for localized prostate cancer.

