9.1 Safety and Efficacy Endpoints

Assessment of early clinical outcomes in focal SBRT for low risk prostate cancer patients. Twenty-four hormone naïve low to intermediate risk prostate cancer patients will be screened for PSA level, acute toxicities and quality of life (QOL) measures at baseline and twelve will be followed at longitudinal follow-up appointments.

Acute and Late GI and GU Adverse Events (AEs)

Adverse events are evaluated by the CTEP Active Version of the NCI Common Terminology Criteria for Adverse Events (CTCAE). We will record in Oncore the highest grade reported during a reporting period. The treatment-related attribution includes definitely, probably or possibly related to treatment. An acute adverse event is defined as the first occurrence of worst severity of the adverse event ≤ 30 days after the completion of RT. We will evaluate the acute radiation therapy-related adverse events. Specifically, we are interested in the percentage of acute GI and GU Grade 3+ adverse events that may occur, which is considered to be similar to the high RT dose arm of RTOG 0126 in terms of RT dose. If our partial prostate hypofractionated regimen has an acceptable percentage, then it will be deemed to have an acceptable adverse event profile. We will report the percentage for the regimen as well as the one-sided 97.5% confidence interval. For example, the number of patients in the high dose arm of RTOG 0126 Phase II reported that 1% of patients experienced Grade 3+ GI/GU acute toxicity, with no patient experiencing Grade 4 or 5 toxicities (citation) should be greater than this pilot study. A late adverse event is defined as the first occurrence of worst severity of adverse event > 180 days after RT completion. Late Grade 3+ GU/GI toxicity information will be collected and reported also.

PSA Failure

Failure occurs when the PSA is first noted to be 2 ng/mL or more than the patient's nadir value post RT completion (Phoenix, Abramowitz 2009). PSA failure at 6, 12 and 24 months following RT will be estimated for the series by the cumulative incidence method (Gray 1988). Also, confidence intervals will be reported.

Disease-Free Survival (DFS)

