10.2 Statistics

Statistical Considerations

Chi-square and cluster re-sampling analyses will be used to correlate suspicion on multiparametric magnetic resonance imaging and the incidence of cancer detected on biopsy.

The primary goal of this study is to evaluate acute and late toxicities. In addition clinical data will be collected to monitor for tumor control. Digital rectal examination (DRE) and serum prostate antigen (PSA) will be evaluated every 3 months for two years. Toxicity will be evaluated EPIC EQ D5, Sexual Medication, Device Screening Questionnaires completed by the patients or in conversation with the patient by the clinical staff, at baseline, 6, 12 and 24 months following the end of radiation therapy (+/- 14 days). Rates of acute and late side effects and adverse events will be summarized as proportions, with 95% confidence intervals.

Biochemical failure will be based on PSA values using the Phoenix definition (clinical nadir +2ng/mL). Data from all patients will be pooled. Survival rates estimated from the Kaplan-Meier curves will be estimated with 95% confidence intervals. We will also track virtual treatment plans based on standard models for treatment to the whole gland versus partial gland MRI-TPUS validated planning to report change in dosimetric parameters of the focal SBRT versus traditional whole-gland treatment plans for statistical comparison.

Either a positive DRE or rising PSA may be used as clinical indication for additional MRI surveillance. When additional MRI are available, tumor volume will be summarized by mean \pm STD and the difference between two time points (pre and post treatment) will be examined using paired T-test. Radiographic efficacy will be summarized by calculating Kaplan-Meier curves for the following: disease-free survival, time to local progression, time to distant failure. Descriptive reports of RECIST (1.1) and volumetric findings will be provided.

Acute/Late Toxicity and Quality of Life Measurements

Using multivariate analysis, we will report acute and late (>180 days post SBRT) rates of GI toxicity with dose-volume histogram. We will also report time to event analyses collected for all available HRQOL data collected.

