Temporal pattern of quality of life scores will be summarized graphically; and repeated measures analysis of variance (ANOVA) will be conducted to test for changes in scores over time. The predictive value of demographic, pathological and clinical factors on the scores will be examined by mixed models assuming missing values are missing at random.

Sample Size

Twelve patients will be evaluated in this pilot study. As a proof-of-principle study, it's not design to have the appropriate power (80%) for detecting significant difference in clinic outcomes (i.e.

toxicities, survival or QOL), but to provide some preliminary data for future studies. A sample of 12 patients, however, achieves 78% power to detect 8% difference of urinary toxicity against historical controls under whole gland therapy using a two-sided binomial test with the target significance level of 0.2. We anticipate that a minimum of twenty four patients will be screened leading to twelve patients who will be treated and evaluated on-study in this pilot study.

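### Sections 2.0 and 9.0 commit 12 single-arm patients to testing equivalent disease control with no margin, reference rate, alpha or decision rule, against an otherwise estimation-only plan

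*Combined protocol and SAP*

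**What the plan says.** Section 2.0 sets out the hypothesis that focal SBRT guided by MRI and histopathology can be used, "leading to equivalent outcomes as whole-gland therapy with reduced toxicity and improved quality of life". The specific aims are introduced as the means of validating it.

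Section 9.0 turns this into an inferential commitment. Focal SBRT "will be evaluated for equivalent efficacy", and the section goes on: "The PSA results along with serial MRI assessments will be used to test the hypothesis of equivalent disease control compared to historical data" for whole-gland SBRT.

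The analysis text does something different:

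- Section 9.1 estimates PSA failure at 6, 12 and 24 months by cumulative incidence with confidence intervals, and disease-free survival (DFS) at the same times by Kaplan-Meier with 95% intervals.
- Section 10.2 repeats Kaplan-Meier estimation with 95% intervals and calls for descriptive RECIST and volumetric reports. There is no control arm: "Data from all patients will be pooled".
- The sample-size text in Section 10.2 states: "Twelve patients will be evaluated in this pilot study". It adds that "it's not design to have the appropriate power (80%) for detecting significant difference in clinic outcomes", with survival among its examples, and that the aim is preliminary data.

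**The concern.** A test of equivalence needs a margin, a reference value, an error rate and a rule for declaring success. None of these is given for disease control. The authors did set thresholds elsewhere: Section 9.0 gives acceptable and unacceptable rates for the EPIC bowel change (35% and 55%) and urinary change (40% and 60%). The only numerical historical outcome rate is for acute toxicity ("1% of patients experienced Grade 3+ GI/GU acute toxicity"), which says nothing about cancer control.

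Two parts of one document therefore promise different things. At stake is what may be concluded about cancer control when part of the gland is left untreated. A study of 12 could report few failures, cite the hypothesis in 2.0 and the test in 9.0, and describe the result as equivalent although the data remain compatible with much worse control.

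**Working it through.** **The plan's own figure.** There is none for disease control. The only power figure, 78% in Section 10.2, concerns an 8% difference in urinary toxicity at a two-sided level of 0.2, with no reference rate stated. It is a separate matter and nothing below uses it.

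**Inputs.** n = 12 treated patients (Sections 4.2 and 10.2); endpoint PSA failure by 24 months (Section 9.1). I assume all 12 are fully observed to 24 months, which favours the plan. The historical failure rate h is not in the documents, so I take h = 2%, 5% and 10% as assumptions.

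**Step 1: the best possible result.** With 0 of 12 failures the exact upper limit is 1 − a^(1/12).

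- One-sided 95% (a = 0.05): 1 − 0.05^(1/12) = 22.1%
- One-sided 97.5% (a = 0.025): 1 − 0.025^(1/12) = 26.5%

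With 1 of 12 failures, the exact (Clopper-Pearson) limits are 33.9% and 38.5%.

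**Step 2: the tightest margin that could be met.** Treating h as fixed and known, 0/12 supports a margin m only if h + m is at least the upper limit. So the smallest m is the upper limit minus h.

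| Assumed h | One-sided 95% | One-sided 97.5% |
|---|---|---|
| 2% | 22.1 − 2 = 20.1 points | 26.5 − 2 = 24.5 points |
| 5% | 22.1 − 5 = 17.1 points | 26.5 − 5 = 21.5 points |
| 10% | 22.1 − 10 = 12.1 points | 26.5 − 10 = 16.5 points |

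Every cell requires zero failures. If the true rate equals h, the chance of 0/12 is (1 − h)^12: 0.98^12 = 78%, 0.95^12 = 54% and 0.90^12 = 28%. A 5- or 10-point margin cannot be met by any result at these rates. For example, with h = 5% and m = 10 points, the chance of 0/12 at the boundary is 0.85^12 = 0.142, above both 0.05 and 0.025.

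**Step 3: if the gap were filled with a difference test.** No such test is written; this shows only what would follow. Use an exact binomial test against h with upper tail at most 0.025.

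- h = 5%: P(X ≥ 2) = 0.118 and P(X ≥ 3) = 0.020, so reject at 3 or more. At a true rate of 10%, P(X ≤ 2) = 89% non-significant; at 15%, 74%; at 30%, 25%.
- h = 10%: P(X ≥ 4) = 0.0256, just over the limit, and P(X ≥ 5) = 0.004, so reject at 5 or more. At a true rate of 20%, P(X ≤ 4) = 93% non-significant. If 4 were allowed to reject, this would be P(X ≤ 3) = 79%.

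A doubled failure rate would usually pass as not significantly different.

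**Step 4: scale.** A single-arm comparison with a 10-point margin, one-sided 0.05 and 80% power needs 38, 59 or 82 patients at h = 2%, 5% or 10%. At one-sided 0.025 it needs 58, 75 or 107.

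**The case against.** The strongest defence is that the operative analyses are already right. An analyst following 9.1 and 10.2 would produce cumulative incidence, Kaplan-Meier estimates and intervals, not a p-value. Section 1.2 presents a feasibility pilot that may lead to later trials, Section 12.2 says safety and effectiveness are unknown, and the publication plan lists early response rather than equivalence. The primary goals named in 9.0 and 10.2 are MRI-histopathology correlation, EPIC scores and toxicity, although the primary-endpoint analysis text under 9.0 opens with treatment efficacy and blurs this.

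Much of that stands, and it limits the harm. It does not remove the conflict. The disclaimer in 10.2 concerns power to detect a difference; it does not withdraw the test in 9.0 or the hypothesis in 2.0. Low power to detect a difference is also exactly what makes finding none uninformative.

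A reader might infer more than the documents support:

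- *That the plan will read a non-significant difference as equivalence.* No difference test for disease control is specified. Comparing the planned interval with a published rate is equally open.
- *That no margin under 20-25 points could ever be met.* That holds only for a historical rate near zero; at an assumed 10% the figure is 12-17 points.
- *That 12 patients can support no equivalence conclusion at all.* As planned none is available, because no margin exists. Numerically, very wide margins could be met with zero failures, and the widest with one.
- *That any true rate would look non-significant.* At an assumed 5%, a true rate of 30% would be missed only about 25% of the time.

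**Conclusion.** The point holds as a conflict between stated purpose and specified analysis. Sections 2.0 and 9.0 claim an inferential property that the design lacks and that 9.1 and 10.2 do not attempt to provide. It should be corrected, but it is an error of wording and not a faulty analysis.

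The limits of 22.1% and 26.5% depend only on n = 12 and complete 24-month follow-up; losses would widen them. The margins and the 89% and 93% figures also depend on the assumed historical rates. Those rates are treated as known without error and as applying to comparable patients, which again favours the plan.

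**What to change.** In Section 9.0, replace the equivalence-test sentence and the phrase "will be evaluated for equivalent efficacy" with:

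> PSA failure (cumulative incidence) and DFS (Kaplan-Meier) at 6, 12 and 24 months will be estimated with 95% confidence intervals, and MRI/RECIST response will be reported descriptively as in 9.2 and 10.2. Any comparison with historical whole-gland data is descriptive, and no test or claim of equivalence will be made.

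This keeps the cumulative-incidence method of 9.1, fixes the confidence level that 9.1 leaves open for PSA failure, and leaves RECIST reporting on the 9.2 schedule (at least 12 and 24 months). In Section 2.0, change the hypothesis from equivalent outcomes to preliminary estimates of disease control. An equivalence question can go to a later trial that states its margin and reference rate.

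The cost is wording in two sections. Patients, procedures, data and sample size are unchanged. The study gives up an equivalence claim that it could not support.

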Focal image-guided radiation therapy is a novel alternative that may provide a cost-effective and less morbid treatment option for men diagnosed with low-risk disease. Conceptually, focal therapy targets only diseased prostatic tissue and spares adjacent non-cancerous prostate tissue which may be as efficacious as whole-gland therapy but with less side effects. Further, clinical evidence suggests that the α/β ratio of prostate cancer is quite low providing an opportunity for greater therapeutic gain with hypofractionated courses of radiotherapy compared to traditional fractionated treatment. The hypothesis of this proposal is multiparametric MR data including T2 weighted, contrast enhanced, and diffusion weighted imaging when correlated with marked histopathology biopsy sites confirming tumor foci, will allow appropriate patient selection for focal radiation therapy with a higher sensitivity than routine MR imaging alone. Further, that using advanced imaging to guide dose modulation in focal stereotactic body radiation therapy (SBRT), also named stereotactic ablative radiotherapy, may provide equivalent outcomes to whole-gland therapy with shortened treatment courses and decreased toxicity. This prospective investigational review board (IRB) approved, single institution pilot study will be used to demonstrate clinical feasibility and may potentially lead to future federally funded Phase I/II and consortium supported multi-center clinical research trials for focal SBRT in localized low-risk prostate cancer patients.

Most recently, parametric sequencing MRI have been reported to identify prostatic regions that are highly suspicious for tumor foci (Valerio 2013). The current study will be used to help select for the proper group of patients for whom focal therapy may be appropriately offered. Men who have a diagnosis of localized prostate cancer with only moderately elevated PSA and Gleason score of 7 or lower without either a dominate pattern 4 or a tertiary pattern 5 seen on initial pathology may be

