For patients who have not previously received a targeted biopsy (in-gantry MRI or US-MRI fusion), during this fiducial marker placement procedure, and just prior to needle insertion to place the fiducial marker, a guided biopsy will be targeted to the location of disease suggested by mpMRI using FDA approved devices for image guided biopsy procedures. An FDA approved sterile surgical needle will be introduced either transrectally or transperineally through which the biopsy needle will pass. Following extraction of tissue sample, a fiducial marker will be placed in each of 3-5 biopsy cavities and recorded for spatial *in-vivo* orientation with to the anatomic and functional image sets (US, CT, MRI and mpMRI).

If additional mapping biopsies are necessary, other sextant regions of the prostate reported as normal by screening MRI will be biopsied as is typical for a mapping biopsy procedure to improve disease staging and localization of true positive disease during the screening procedure. Thus, a total of 12 to 15 biopsies will be obtained from each patient for screening eligibility to aid in a determination of likelihood that disease is not multifocal and to enable delivery of focal partial organ therapy. Each biopsy site will be tracked using a combination of permanent and virtual fiducial markers. Virtual markers will be electronically tracked in the regions suggested to be negative for the presence of disease on imaging at the sites of all other sextant biopsy locations using the biopsy needle tip as a temporary fiducial imaged by ultrasound at the time of biopsy and fused back to the mpMRI and planning CT scan if the patient goes on to be treated on protocol.

It should be noted that the permanent fiducial markers placed for screening would not preclude prostatectomy, or could be used for directing radiotherapy if the patient is found to be ineligible for

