
Multiparametric and Magnetic Resonance Imaging (mpMRI)

Prior to radiation therapy, all patients will have standard of care staging and treatment planning MRI's of the pelvis, with contrast unless clinically contraindicated, using standard morphologic imaging sequences, per institutional standard of care imaging protocols for anatomic detail and localization. Additional functional mpMRI sequences will also be acquired and evaluated to enable morphologic and/or quantification of various tissue parameters as are routinely ordered prior to radiation therapy. The duration of the entire mpMR imaging procedure (patient on the scanner table) will be no longer than a total of 90 minutes, which is within the range for a standard single diagnostic MRI scan. Quantitative MRI data may include analysis of some or all of the following parameters:

Diffusion weighted imaging (DWI):

- Measurement of b-value assesses different levels of diffusivity within tumor tissue and normal tissue.
- Apparent diffusion coefficient (ADC) will be calculated as a quantitative measure from multiple b-values by measurement of ROI in the target lesion.

Dynamic contrast enhanced MRI (DCE-MRI):

- Typical quantitative parameters will be obtained describing tissue enhancement pattern and perfusion, contrast agent exchange rates of tissues and distribution of contrast between the various tissue spaces using standard evaluation models.
- Quantitative assessment will be performed with post processing techniques as commercially available as well as post processing software under investigation or development to demonstrate feasibility with currently available and future techniques.

These sequences will be recorded for virtual comparison to the standard MRI sequences to determine if the investigational functional data correlates with histopathology data, and to determine if these data would have changed the radiation therapy contouring and dose delivery. Any change in treatment planning due to functional MRI versus standard sequences alone will be recorded, and evaluated for utility in the determination of tumor response to therapy.

Target Delineation

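### The MRI-histology chi-square ignores the order of suspicion grades, and the promised accuracy comparison of multiparametric with standard MRI has no paired estimate

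*Combined protocol and SAP*

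**What the plan says.** Under Analysis of the Primary Endpoints, section 9.0 states: "Chi-square and cluster analysis will be used to correlate degree of suspicion on MR pulse sequences with incidence of cancer detected on biopsy". Section 10.2 gives a near-duplicate: "Chi-square and cluster re-sampling analyses will be used to correlate suspicion on multiparametric magnetic resonance imaging" and the cancer found on biopsy. It names multiparametric MRI only, with no comparator.

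Three other places bear on what the analysis should deliver:
- Section 2.0, aim 1, is a correlation aim: "Evaluate the correlation of histopathology findings in comparison to regions of the prostate reported to be suspicious for harboring tumor burden" on multiparametric MRI.
- Section 9.0 says that the confirmed targets "will be evaluated for reporting accuracy of multiparametric and standard MRI sequences to detect disease". Both sequence sets are named, but no measure of accuracy, cut-off or interval.
- Section 6.1.1 says of the functional sequences: "These sequences will be recorded for virtual comparison to the standard MRI sequences". So both sets come from the same men, and a comparison is intended.

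Section 1.2 also contains a hypothesis that multiparametric data, correlated with marked biopsy sites, "will allow appropriate patient selection for focal radiation therapy with a higher sensitivity than routine MR imaging alone".

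On sampling, section 6.1.1 says that "a total of 12 to 15 biopsies will be obtained from each patient" and that "other sextant regions of the prostate reported as normal by screening MRI will be biopsied". The latter is introduced as applying where additional mapping biopsies are needed.

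**The concern.** Section 9.0 calls the MRI-histology mapping the primary goal (section 10.2 gives that place to toxicity). Two features of the planned analysis fit the stated intentions poorly.

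First, degree of suspicion is a graded quantity. A general chi-square treats the grades as unordered labels, so it spreads its power over patterns that nobody expects.

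Second, the promised accuracy of two readings of the same regions in the same men calls for sensitivity, specificity and a within-region difference. A chi-square of one reading against biopsy shows only that the reading is associated with cancer. The study could report a small p-value and still say nothing about whether the functional sequences add to the standard ones, although it collects the images for that question.

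**Working it through.** **Inputs.** From the documents: 24 screened and 12 enrolled (section 4.2); MRI and histology data from all consented and screened men (section 9.1); 12 to 15 cores per man (section 6.1.1). The documents give no suspicion scale, alpha, effect size or power for this aim, so there is no plan figure to reproduce. The 78% power in section 10.2 is for urinary toxicity. All rates below are assumptions.

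**1. Order is ignored.** Take five grades with cancer/no cancer counts 10/50, 8/32, 9/21, 6/9 and 7/3. The Pearson chi-square is 15.38 (p = 0.004) and the Cochran-Armitage trend statistic is 13.12 (p = 0.0003). Shuffle the grade labels: Pearson stays at 15.38, while the trend statistic falls to 1.98 (p = 0.16). The Pearson test remains valid but cannot tell a gradient from a scramble.

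**2. Cost in power.** Set the noncentrality at 7.85, which gives a 1-df trend test 80% power at two-sided 0.05. If risk follows the trend scores, the general chi-square has the same noncentrality on more degrees of freedom:

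| Grades | df | Power |
|---|---|---|
| trend test | 1 | 80% |
| 3 | 2 | 71% |
| 4 | 3 | 64% |
| 5 | 4 | 60% |

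With only two grades, both tests have 1 df and nothing is lost.

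**3. Association does not track sensitivity.** Take 180 cores (12 men × 15), 24 of them positive:

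| Reading | Sensitivity | Specificity | Chi-square |
|---|---|---|---|
| A | 18/24 = 0.75 | 126/156 = 0.81 | 33.1 |
| B | 22/24 = 0.92 | 106/156 = 0.68 | 30.8 |
| C | 18/24 = 0.75 | 141/156 = 0.90 | 59.4 |

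B is more sensitive than A but has the smaller chi-square. C is no more sensitive than A but has much the larger one. Setting one chi-square beside another would not show which reading finds more cancer.

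**4. Value of pairing.** Assume sensitivities 0.80 and 0.65, with correlation phi between readings of the same positive region. The variance per region is 0.16 + 0.2275 = 0.3875 unpaired, and 0.3875 − 2·phi·√(0.16 × 0.2275) = 0.3875 − 0.3816·phi paired. The ratio of standard errors, unpaired to paired, is:
- phi 0.3: √(0.3875/0.2730) = 1.19
- phi 0.5: √(0.3875/0.1967) = 1.40
- phi 0.6: √(0.3875/0.1586) = 1.56

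The plan proposes no unpaired comparison. These ratios show what pairing gains once a comparison is made.

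**5. Precision to expect.** With discordant proportions 0.20 and 0.05 (difference 0.15, phi about 0.42), the standard error is √((0.25 − 0.15²)/m) = √(0.2275/m) for m independent positive foci. The 95% half-width is 0.27 for m = 12, 0.19 for m = 24 and 0.13 for m = 48. Exact McNemar power at two-sided 0.05 is 1.4% for 12 foci, 15% for 24 and 46% for 48. At least six discordant foci, all in one direction, are needed for p ≤ 0.05 (2 × 0.5⁶ = 0.031).

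**The case against.** The strongest reply is that the plan does what its formal aim asks. Aim 1 is a correlation, and a chi-square addresses correlation. Chi-square may be shorthand that includes a trend version, and section 10.2 speaks of suspicion without grading it; if the reading is binary, nothing is lost. Accuracy of both sequence sets is promised separately. Section 10.2 describes a proof-of-principle study without conventional power. Much of this stands: the fault is under-specification and a less efficient test, not an invalid one.

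Three stronger inferences are tempting and are not supported:
- *Ignoring order is why sensitivity goes unassessed.* It is not. Order costs power on the graded question; the missing comparison is a separate gap.
- *Multiple cores per man are overlooked.* Section 10.2 names cluster re-sampling, which can handle them.
- *A paired comparison of the two sequence sets would test the section 1.2 hypothesis.* That hypothesis concerns patient selection using multiparametric MRI together with marked histology. A comparison with biopsy as the reference standard answers a different question.

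A further caution concerns the repair itself. Targeted cores follow the multiparametric reading, and sampling of MRI-normal sextants is worded as conditional. The stated 12 to 15 cores for each man suggest wide sampling, but the condition remains. Lesions missed by the multiparametric reading may be under-sampled, which could favour it.

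**Conclusion.** The concern holds in a limited form. The named analysis answers the correlation aim, loses power if suspicion is graded, and leaves the promised comparison of multiparametric with standard sequences without an estimand or interval. The loss is about 9 to 20 percentage points of power from a reference of 80%, for three to five grades, assuming monotone risk that follows the trend scores and alpha 0.05. Pairing narrows the standard error of a sensitivity difference by a factor of 1.2 to 1.6 under the assumed 0.80 and 0.65 with phi 0.3 to 0.6. Neither range comes from the documents. With about 24 screened men, a designated McNemar test would have little power, so the paired comparison belongs in the plan as estimation. This is a cheap improvement, not a flaw that invalidates the study.

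**What to change.** Amend sections 9.0 and 10.2 in the same words:

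1. For graded suspicion, replace the general chi-square with a trend test or a clustered ROC area, and state the suspicion scale. Use the cluster re-sampling already named in section 10.2, with the man as the cluster, and bring the cluster analysis wording of section 9.0 into line.
2. Report sensitivity and specificity of multiparametric MRI and of standard sequences on the same biopsied regions, with the paired differences and by-patient re-sampled 95% intervals. State one positivity cut-off and whether the unit is the region or the core. Label the results as estimates, neither a powered test nor the test of the section 1.2 hypothesis.
3. Record the standard-sequence reading separately, by region, for the comparison in section 6.1.1.
4. State that sensitivity is conditional on the regions biopsied and may favour multiparametric MRI, for the sampling reasons in section 6.1.1.

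The cost is mainly wording and a little more analysis. No new scans or biopsies are needed, but separate standard-sequence readings add reading time if they are not already made. The trend test is weaker if risk is not monotone in the grade, and the paired intervals will be wide.
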